⁴⁴ health behavior adherence (e.g., smoking cessation and risky drinking),⁴⁵⁻⁴⁷ and outcomes (e.g., lung cancer death rates and sobriety). A-CHESS is consistent with respected health behavior change models such as self-determination theory (SDT)⁴⁸ and Marlatt's Cognitive Behavior model⁴⁹ of relapse prevention. In a randomized trial (N=349), patients using A-CHESS, compared to those in the control group, reported 51% fewer risky drinking days in the prior 30 days at the 4-, 8-, and 12-month follow-ups (mean of 1.39 days in A-CHESS vs. 2.75 days per month in TAU, $p = .003$). Rates of alcohol abstinence were significantly higher among A-CHESS patients at 8 months (78% vs. 67%) and 12 months (79% vs. 66%).⁵⁰ The A-CHESS app includes educational materials, discussion groups, links to SUD resources and weekly self-monitoring for patients. The CHESS platform has also been an effective method for clinicians to interact with their patients.⁵¹ A-CHESS provides a report for clinicians that delivers to the clinician team information about worrisome changes in symptoms collected from the patient during self-monitoring of risk-related items (i.e., sleeping problems, depression, urge, risky situation and relationship troubles).⁵² A-CHESS contacts the clinical team by email, phone, or fax (according to clinician preference) whenever a threshold symptom is reported. The alert was intended to quickly bring clinician attention to emerging symptoms.

Technology like A-CHESS is a potential game changer: it can provide recovery supports 24 hours a day, 7 days a week and can be customized to individual needs. **This research will test a technology adoption framework to increase use of the A-CHESS smartphone app.** A supplemental study will help understand how A-CHESS may help patients manage increased levels of anxiety and loneliness during the COVID-19 pandemic.

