2. STUDY OBJECTIVES

The specific aim of this study is to compare the effectiveness of NIATx-TI (Arm 2) and Product Training (Arm1) in implementing an evidence-based innovation (A-CHESS). Impact will be measured using the RE-AIM framework:⁵³

- Reach or Participation (Primary Outcome): a) percent and representativeness, based on age, gender, and ethnicity by organizational site, and b) A-CHESS use per each counselor, by days of use;
- Effectiveness: retention rates of eligible patients overall

- Adoption: percent and representativeness, based on age, gender, race, ethnicity, and education level of counselors referring and not referring patients to A-CHESS;
- Implementation: a) organizational readiness for, and b) fidelity of A-CHESS implementation; and c) qualitative and d) cost effectiveness analyses to develop a better understanding of the implementation processes for delivering NIATx-TI compared to product training alone; and
- Maintenance: A-CHESS use (e.g., A-CHESS downloads and days of A-CHESS use) during the post-test phase.

The specific aims of the COVID-19 supplemental study are 1) to understand whether using A-CHESS may help patients manage anxiety and loneliness associated with social isolation, physical distancing, and other changes to daily life during the COVID-19 pandemic, and 2) to understand how patients have adapted to changes in treatment modality during the COVID-19 pandemic. Impact will be measured by offering all patients who have ever signed up for an A-CHESS account the chance to complete an online survey (administered through REDCap) as well as the opportunity for a qualitative interview with a member of our research team using a standardized interview guide.

Study Coordination

The UW-Madison Center for Health Enhancement Systems Studies (CHESS) is the coordinating site for this study. The UW study coordinator will oversee all recruitment activities which includes:

- developing organizational site-specific recruitment and data collection processes that meet study objectives;
- training staff on protocol procedures prior to start of recruitment and continuous monitoring to assure compliance with the protocol and human subjects regulation;
- communicating with clinic site staff as needed via conference calls to monitor progress, inform of protocol changes/distribute new version of protocol, and address unanticipated issues or challenges;
- and manage all study data.

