The organizational survey will be completed by a member of the management team. The staff surveys will be completed by staff that are invited to complete the survey by the site coordinator. (The site coordinator's role in the clinic may be an administrative support position in the quality or staff training departments, a member of clinical supervision, or management.) The site coordinator will inform the staff person that survey completion is optional, and the consent form that precedes the survey in REDCap will also state that survey participation is optional. The site coordinator does not have access to the survey data nor will they receive any data feedback or summaries from the surveys. The consent form will describe that completing the staff or organizational survey infers their consent. For those who do not complete the survey, the survey will not be recorded and no record of the person not wanting to participate will be made.

Patient COVID-19 Supplemental Redcap Survey and Interview Recruitment:

All patients who have signed up for an A-CHESS account will be contacted via email and invited to complete a supplemental survey about their experiences during the COVID-19 pandemic. It will be necessary to collect patient's names and email addresses in order to link their survey responses to passively collected app usage data. Patients will then complete an approximately 30-minute online survey through REDCap. Participants will be remunerated \$25 for their time. At the end of the survey, participants will be asked whether they are interested in being contacted by a member of the research team to participate in a follow-up, in-depth interview. A research assistant will contact interested participants and set up a time to conduct an approximately 30-minute interview. Research assistants will go over an informed consent document, and participants will need to consent to interviews being recorded. Participants will be remunerated an additional \$25 for their time.

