% who download A-CHESS app and frequency of A-CHESS use in days	Gustafson et al. ⁵⁰	A-CHESS Server - Monthly (Ms 11 - 47) IDPH – Monthly (Ms11 - 47)
Adoption		
% Counselor Using A-CHESS	Knight et al. ⁵⁹	Organizational Survey & A-CHESS Logs
Effectiveness		
Retention (Length of Stay)	Simpson et al. ⁶¹	IDPH- Ms 11 - 50
Maintenance		
Finance Resource Availability	Klein ⁶²	Organizational Survey – Ms 12, 30

Measurement	Measure Source	Data Source/Frequency (for Cohort 1)
A-CHESS Implementation Fidelity	Developed for this trial	Staff Survey – Ms 12, 30
Organizational Change Manager (OCM)	Gustafson et al. ⁶³	Staff Survey – Ms 11, 12, 30
Patient COVID-19 Survey		
Patient socio-demographic and descriptive characteristics: age, race/ethnicity, sex, gender, sexual orientation, education, marital status, income, housing, family size, employment status, health insurance	PhenX repository	Patient COVID-19 Survey – once during March 2021
Criminal justice history	Justice Community Opioid Involvement Network	
Alcohol Use Disorder Severity	Saunders et al.; Babor et al.	
Substance Use Disorder Severity	Skinner	
Loneliness	Hays & DiMatteo	
Anxiety	Cella et al.	
Substance use disorder recovery strengths	Vilsant et al.	
COVID-19 risk and protective behaviors and impact on daily living	Adapted from several COVID-19 surveys	

Qualitative Interviews: Qualitative data will be gathered from organizational staff at four points. Qualitative interviews with clinicians and peer recovery support staff will occur during the intervention phase. The goal of the interviews is to gain a better understanding of patterns with app adoption and use. Phone interviews of up to 30 minutes will be conducted with approximately 15 people at various sites. The interviews will be audiotaped (with participant permission), but the staff person's identity will be protected and in no way be linked to results.

Additionally, the study, interviews with staff from a randomly selected site in all organizations will occur at the end of intervention phase and again at the same site at the end of sustainability phase. The intent of the surveys is to gain a retrospective understanding of what occurred during implementation. Phone interviews of up to 30 minutes will be conducted with up to four people in at each site. The interviews will be audiotaped (with staff participant permission), but the staff person's identity will be protected and in no way be linked to results.

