Use data: A-CHESS use data will be collected monthly to assess the percentage of eligible patients who download the A-CHESS app per month per site and the frequency of use by app user. For the percentage who download A-CHESS, data will be collected during the 18-month intervention period and 6 months of post-intervention period for that organization. Frequency of use data for an individual user will be collected during the 12-month period following initial use of A-CHESS. The app automatically collects use data by placing "cookies" on patients' smartphones (with patients' consent) when they enroll in the study. Data are stored on a central server at CHESS. Electronic data, such as A-CHESS use data, will be stored on a secure DoIT server which is backed up according to a standard protocol. Access to this data will be limited by granting individuals access via their UW user log-in.

The Iowa Department of Public Health (IDPH) will also provide data available through existing IDPH administrative databases. A preliminary analysis of *organizational* data will compare baseline characteristics between the NIATx-TI and Product Training alone organizations, as well as organizations enrolled in the project and eligible organizations not participating (Admissions, Rural v. Urban, and Gender/Age/Ethnicity, and Poverty Level), using the National Survey of Substance Abuse Treatment Services (N-SSATS)⁵⁵ and Treatment Episode Data Set (TEDS)⁵⁶ data definitions.

During the study, IDPH will provide *patient* demographic data (gender, age, and ethnicity, using TEDS definitions) for all patients by organizational site. As part of the organizational survey, we will include questions about *counselors'* gender, ethnicity, and race.

Retention data will be collected by IDPH and provided monthly using existing data.

We will use UW Box to store data received from IDPH.

Supplemental COVID-19 Study – Patient Surveys and In-Depth Interviews

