We will create and distribute an information sheet for staff giving them the option to decline to participate in the trial or A-CHESS distribution.

Organizational Data: We will assess Financial Resource Availability Inventory, A-CHESS Implementation Fidelity, and List of Counselors (for counselor A-CHESS participation rates) at two points during the study - at organizational baseline (M 11 - 14) and end of the intervention period (M30 - 33) (M=months are in a range due to the 4 study periods) The Iowa Department of Public Health (IDPH) will provide, by site, aggregate data on Admissions, and Rural v. Urban. This data will be collected from IDPH databases at months 11, 22, 34, and 42

Consumer level: Eligible consumers will be identified in real time during their first three outpatient appointments with a participating SUD treatment site. Site counselors will provide information about the study. If the patient is interested in the study, the counselor will provide a brief introduction to A-CHESS and provide information to the client with the URL to download A-CHESS. If the patient chooses to participate, informed consent will be documented via an IRB-approved consent form on the A-CHESS app.

To be eligible for A-CHESS, SUD consumers must: 1) be >18 years old; 2) understand and agree to an English language consent form via the A-CHESS app; 3) have access to a mobile smartphone, and 4) have an SUD diagnosis.

We anticipate enrolling consumers to use A-CHESS (approximately 43 per organizational per site, for a n=1,800 for the study). The state (IDPH) will provide de-identified data including gender, age, ethnicity, poverty level, and units of service for each site.

During approximately March 2021, all patients who have signed up for an A-CHESS account (to-date n=520) will be invited to participate in a one-time, online, self-report survey through REDCap.

Sources of Materials

All data will be coded before reaching evaluation staff. These include data collected by A-CHESS App server on A-CHESS use as well as organization and staff interview and qualitative survey data. Coding of consumer and counselor/staff data will take place, where necessary, by replacing identifying information (such as consumer and staff names) with code numbers prior to data analysis. A unique study ID number will be assigned to all patient surveys and in-depth interviews. Names collected through the informed consent process will be stored separately.

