Analysis of Supplemental COVID-19 Patient Survey and In-Depth Interview Data: Patient survey data will be matched with longitudinal app usage data. We anticipate using linear regression models to quantify the association between app usage (modeled continuously and binary as an indicator of meaningful use of A-CHESS) and several continuous outcomes based on validated measure – anxiety (PROMIS 29) and loneliness (UCLA Loneliness Scale-8). We will adjust for potentially confounding variables, including socio-demographic characteristics, recovery capital, criminal justice involvement, and substance use disorder severity. Further, we will use logistic or log-binomial regression models to assess how app usage is associated with substance use disorder treatment participation (e.g., AA/NA/self-help group participation, attendance at group therapy).

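### App-use data are planned for only 12 months after first use, so for COVID-19 survey respondents who joined before about March 2020 recorded use stops before the March 2021 survey

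*Combined protocol and SAP*

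**What the plan says.** The supplement's first aim, in section 2, is "to understand whether using A-CHESS may help patients manage anxiety and loneliness associated with social isolation" and other pandemic changes. Section 7 adds that the survey will assess whether app use softened the effect of COVID-19 on these two outcomes.

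The outcome is measured once. Table 1 in section 5 lists "Patient COVID-19 Survey – once during March 2021". The Study Design text in the same section says "During approximately March 2021, all patients who have signed up for an A-CHESS account (to-date n=520) will be invited". Join date is not restricted.

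The exposure comes from app records. Section 4 explains that identifiers are needed to "link their survey responses to passively collected app usage data". Section 9 says "Patient survey data will be matched with longitudinal app usage data" and enters app use in the models both as a continuous variable and as a binary indicator of meaningful use. It names no start or end date for the use that counts.

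The Use data text in section 5 says "Frequency of use data for an individual user will be collected during the 12-month period following initial use of A-CHESS". Section 8 gives patients the app for the whole study, so use can continue after that period closes.

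**The concern.** The aim concerns app use during the pandemic, but the collection rule follows each person's first use and not the calendar. Followed as written, the two do not line up, with three consequences.

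- Someone who joined before about March 2020 and kept using the app has no planned use record for the months just before the survey. An active user can look inactive for part of the pandemic.
- Use before the pandemic counts the same as use during it, because no window separates them.
- If exposure is total recorded use, which the plan allows, it depends on join date. An early joiner contributes 12 months and someone who joined shortly before the survey contributes weeks.

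The exposure would then be misclassified in a way tied to when a person entered treatment. The resulting bias in the association has no predictable direction.

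**Working it through.** **Is the 12-month limit operational?** Table 1 gives server collection for Cohort 1 as months 11 to 47. The inputs are a start at month 11 (Table 1), 18 months of intervention plus 6 further months of recruitment (section 3), and 12 months of use data per person (section 5):

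11 + 18 + 6 + 12 = 47.

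This reproduces the plan's figure exactly. The month-47 end date is a cohort-level span that already contains the 12-month limit. It does not override it.

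**Individual windows.** Window end = join month + 12. Gap = March 2021 minus window end. The documents give no pandemic start. I assume March 2020 (12 months to the survey) and show January 2020 (14 months) beside it.

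| Joined | Window ends | Gap to survey (months) | Pandemic months recorded, March 2020 start | January 2020 start |
|---|---|---|---|---|
| Oct 2018 | Oct 2019 | 17 | 0 of 12 | 0 of 14 |
| Mar 2019 | Mar 2020 | 12 | 0 of 12 | 2 of 14 |
| Sep 2019 | Sep 2020 | 6 | 6 of 12 | 8 of 14 |
| Feb 2020 | Feb 2021 | 1 | 11 of 12 | 12 of 14 |
| Mar 2020 | Mar 2021 | 0 | 12 of 12 | 12 of 14 |

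Only the gap column follows from the documents alone. Which of these join months actually occurred is not stated.

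**How many people?** The 520 account holders are the only count given. Assume they signed up at a steady rate over L months ending in March 2021, with a pandemic start of March 2020.

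- Window closed before the survey: 520 × (L − 12)/L, or 0 if L ≤ 12.
- Window wholly before the pandemic: 520 × (L − 24)/L, or 0 if L ≤ 24.

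| L (months) | Closed before survey | Wholly before pandemic |
|---|---|---|
| 12 | 0 | 0 |
| 18 | 520 × 6/18 = 173 (33%) | 0 |
| 24 | 520 × 12/24 = 260 (50%) | 0 |
| 30 | 520 × 18/30 = 312 (60%) | 520 × 6/30 = 104 (20%) |

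**How much is missing among those with closed windows?** The gap is spread evenly from 0 to L − 12 months, and at most 12 pandemic months can be lost.

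- L = 18: mean of 0 to 6 = 3 of 12 months.
- L = 24: mean of 0 to 12 = 6 of 12 months.
- L = 30: (12/18) × 6 + (6/18) × 12 = 8 of 12 months.

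**The case against.** The strongest reply is that the limit was written for the main study's Reach measure and covers frequency of use only. The app logs use automatically to a central server, and the supplement describes its source as passive, longitudinal use data without stating a limit. Logs past 12 months may well exist. A reader might infer from the limit that such data do not exist, and the documents do not support that. But no section plans to collect or use later records for the supplement, so the possibility makes the repair easier without correcting the plan.

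Other stronger readings also fail.

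- A reader might infer that anyone who joined before March 2020 has no recorded pandemic use. That is false for most such joiners: with a March 2020 start, a February 2020 joiner has 11 of 12 months.
- A reader might infer that the earliest users' records do predate the pandemic. That needs first use before about March 2019 (about January 2019 if the pandemic is dated from January 2020). No enrolment is dated and study months are not tied to the calendar. The staff consent version code, 092518, can be read as September 2018. That makes such early use possible but does not establish it.
- A reader might infer that a large share of respondents is affected. The counts above rest on assumed accrual, include people with only a short gap, describe account holders and not respondents, and can be zero.
- A reader might add that, without an earlier measure of distress, the app will look harmful because distressed people use it more. The models do lack such a measure, but people who are doing well may also use the app more, so no direction follows. The obvious proxy is weak. The weekly self-monitoring covers "risk-related items (i.e., sleeping problems, depression, urge, risky situation and relationship troubles", with no anxiety or loneliness item. Answering is voluntary and is itself app use, so light users would be the ones missing.

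It is also fair that this is an observational add-on with tentatively worded models.

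**Conclusion.** The mismatch stands. A stated 12-month rule, a single survey of all account holders and an analysis with no exposure window together mean that, as written, recorded use stops before the outcome for anyone who joined before about March 2020. For anyone who joined before about March 2019, if there were any, it would miss the pandemic altogether.

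The number affected is unknown. It runs from none to 312 of 520 for closed windows, and from none to 104 for windows wholly before the pandemic. This range assumes steady sign-up over 12 to 30 months to March 2021, a March 2020 pandemic start, and 520 as the final count of account holders, although the protocol gives that figure only as the count to date.

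The change is worth making because the supplement's first aim depends on this exposure. The randomized comparison and the main trial's primary outcome are not touched.

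**What to change.** Reconcile the supplement analysis in section 9 with the Use data text in section 5:

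1. For the supplement, extend use data to the survey date for all account holders, from existing server logs, after checking that consent covers monitoring beyond 12 months.
2. Define exposure as a rate, days of use per month available, from March 2020 (or sign-up, if later) to the survey. Apply the same window to the binary indicator of meaningful use. Raw days would reintroduce the dependence on join date.
3. Adjust for time since sign-up.
4. If later logs cannot be used, restrict the main supplement model to people whose window covers the survey period, and say so.
5. Do not make the weekly reports a required covariate. At most, use them in a sensitivity analysis.

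The cost is a longer data pull, a consent check and a few sentences in the analysis plan. The fallback in step 4 costs more. Under the 18-, 24- and 30-month assumptions it leaves 347, 260 or 208 of the 520 account holders (520 minus 173, 260 or 312) before non-response, and it confines the result to more recent joiners.

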3. SELECTION OF SUBJECTS

This study will engage SUD organizations, counseling and peer recovery support specialist staff at those organizations, and patients of those organizations.

Organizations: Sixteen SUD organizations in Iowa, with a total of forty sites, have agreed to participate in the project.

Counselors: The site coordinator will invite all outpatient counselors serving adult patients employed by the 16 SUD organizations to be part of the study as part of their role in the participating organizations. Any counselor may formally decline to participate during the training or any time thereafter.

Peer Recovery Support Specialists: Peer Recovery Support Specialists associated with the organization will be invited to be part of the study. Any Peer Recovery Support Specialists may formally decline to participate during training or any time thereafter.

Patients: We will aim to enroll 1,800 outpatients from the 16 enrolled organizations. Each organization is expected to have about 516 A-CHESS-eligible patients on average. We estimate that we will recruit a conservative 30% (or approximately 43 per organizational site) for a total n=1,800 patients in the study. We will recruit patients for the 18-month intervention period plus 6 months into the maintenance period. Patients are eligible for the study if they:

- Are 18+ years old
- Understand English
- Have a SUD diagnosis
- Have access to a smartphone

All patients will be offered the opportunity to complete a survey through REDCap. To date, n=520 patients have created an A-CHESS account. We will also conduct in-depth interviews with 40 patients who have created an A-CHESS account.

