9. STATISTICAL CONSIDERATIONS

Sample Size, Power & Data Analysis Plan: We will fit a mixed-effects model with the appropriate link function (e.g., linear, log) to the monthly results for the performance measures, % of eligible A-CHESS users and frequency of A-CHESS use, for each of the participating organizational sites, clustered by organization, and estimate the NIATx-TI framework and

product training effects. A mixed-effect model offers 2 advantages over conventional regression models: 1) The mean outcomes for a given treatment organization are expected to be correlated from month to month. A mixed-effect model allows for auto-correlated error terms. 2) Many unobservable treatment organizational site characteristics are likely to influence the key measures. Random effects at the treatment organization site level can be employed within the mixed-effect model to capture the correlation introduced by such characteristics. Proper reflection of auto-correlation and random effects allows for more reliable estimates of the fixed effects, starting at baseline, then again during the 18-month test and post-test periods. The power of the study design is determined by the anticipated standardized effect size based on effects experienced in the IRHIT project. The standardized effect size is calculated following Cohen's definition of mean effect size divided by effect size standard error.⁶⁵ The higher the standardized effect size, the more powerful the study design. Historically, cluster-randomized trials portray the standardized effect sizes of 0.2, 0.5 and 0.8 as small, medium, and large respectively. The IRHIT pilot data found that NIATx-TI increased client technology use rates by 12.4% (increase of intervention success), which can be transformed into Cohen's $d = 0.352$.⁶⁶ Intraclass correlation (ICC) among sites affects the power of cluster-randomized trials.⁶⁷ An estimate of ICC is around 0.10.⁵⁰ With a total of 8 organizations, with 20 organizational sites in each arm, where each site has an average 62 eligible patients, the study will achieve a power of .90 with a type I error rate of 0.05.

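### The COVID-19 survey regressions name no adjustment for site, organization or arm, so standard errors are likely too small if both app use and outcomes cluster

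*Combined protocol and SAP*

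**What the plan says.** The survey analysis is in section 9 of the combined protocol and SAP, under the supplemental COVID-19 patient survey and interview data. For anxiety and loneliness: "We anticipate using linear regression models to quantify the association between app usage" and the outcomes. For participation in treatment: "we will use logistic or log-binomial regression models to assess how app usage is associated with substance use disorder treatment participation". The exposure is measured on each patient: "app usage (modeled continuously and binary as an indicator of meaningful use of A-CHESS". On covariates: "We will adjust for potentially confounding variables, including socio-demographic characteristics, recovery capital, criminal justice involvement, and substance use disorder severity". All the named covariates belong to the patient. Site, organization and arm are not among them, and no random effect, generalized estimating equation or robust variance is mentioned.

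The survey goes to everyone who has opened an account. Section 3 gives the count ("To date, n=520 patients have created an A-CHESS account") and the structure they come from ("Sixteen SUD organizations in Iowa, with a total of forty sites"). Section 8 randomizes organizations within matched pairs.

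Elsewhere in section 9 the nesting is handled. The Reach model covers sites clustered by organization, with this reasoning: "Random effects at the treatment organization site level can be employed within the mixed-effect model to capture the correlation introduced by such characteristics". Retention is compared with hierarchical models. Neither provision is extended to the survey.

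**The concern.** The Reach paragraph of section 9 treats frequency of A-CHESS use as an outcome that unmeasured site characteristics are likely to influence. In the survey models that same use becomes the regressor. It is also what the organization-level strategy is designed to raise, so some clustering of the exposure follows from the plan's own premise. Clustering of the outcomes is plausible but not documented. Group-therapy attendance, for example, may depend on what a clinic offers.

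Two consequences could follow. First, if use and outcome both cluster, ordinary regression standard errors understate the uncertainty. Second, whatever the variance does, arm, organization and location may be related to both use and outcome. If so, leaving them out can bias the coefficient itself. At stake is the only stated quantitative test of the first COVID-19 aim in section 2, whether A-CHESS use may help patients manage anxiety and loneliness.

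**Working it through.** **The plan's own figure.** The only power figure is for the main trial (section 9): 20 sites per arm, 62 eligible patients per site, ICC 0.10, d = 0.352, type I error 0.05 (taken as two-sided).

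- Design effect: 1 + (62 − 1) × 0.10 = 7.10.
- Effective number per arm: (20 × 62)/7.10 = 1240/7.10 = 174.6.
- Power: 0.908 by the normal approximation and 0.893 by noncentral t with 38 degrees of freedom, against 0.90 stated.

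The figure reproduces, so the plan does allow for a site-level ICC of 0.10 in its main comparison. It gives no sample size, power, significance level or ICC for the survey.

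**Inputs for the survey.** Account holders: 520 (section 3). Clusters: 40 sites or 16 organizations (section 3). Mean cluster size if all respond: 520/40 = 13 per site, 520/16 = 32.5 per organization. Assumed: the response rate, the ICC of use (ρx) and the ICC of the outcome (ρy).

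**Formula.** For a slope on a patient-level exposure with exchangeable clustering, equal clusters and no covariates:

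- variance inflation D = 1 + (m − 1) × ρx × ρy
- true SE / naive SE = √D
- actual two-sided error at nominal 0.05 = 2 × [1 − Φ(1.96/√D)]

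| ρx | ρy | Cluster | D | SE ratio | Type I error |
|---|---|---|---|---|---|
| 0 | any | either | 1.00 | 1.00 | 0.050 |
| 0.05 | 0.05 | organization | 1 + 31.5 × 0.0025 = 1.079 | 1.04 | 0.059 |
| 0.10 | 0.10 | site | 1 + 12 × 0.01 = 1.12 | 1.06 | 0.064 |
| 0.10 | 0.10 | organization | 1 + 31.5 × 0.01 = 1.315 | 1.15 | 0.087 |
| 0.30 | 0.01 | organization | 1 + 31.5 × 0.003 = 1.095 | 1.05 | 0.061 |
| 0.30 | 0.05 | organization | 1 + 31.5 × 0.015 = 1.472 | 1.21 | 0.106 |
| 0.30 | 0.10 | site | 1 + 12 × 0.03 = 1.36 | 1.17 | 0.093 |
| 0.30 | 0.10 | organization | 1 + 31.5 × 0.03 = 1.945 | 1.39 | 0.160 |

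**Simulation check.** With 4000 replicates per scenario and both ICCs 0.10, the SE ratio was 1.05 and the error 0.065 for 40 clusters of 13, and 1.13 and 0.085 for 16 clusters of 32. These agree with the formula.

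**Sensitivity.**

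- With half responding (260) and both ICCs 0.10, the ratios fall to 1.03 by site (m = 6.5, D = 1.055) and 1.07 by organization (m = 16.25, D = 1.153).
- Unequal clusters push the other way. With an assumed coefficient of variation of 0.6, replacing m by 32.5 × (1 + 0.36) = 44.2 gives D = 1.432 and error about 0.10 at 0.10/0.10. At 0.30/0.10 it gives D = 2.296 and error about 0.20.

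**The case against.** The plan nowhere asserts independence. It speaks of what it anticipates, and its covariate list is open-ended, so site or arm could still be added. That is correct. The point is therefore that the models as specified leave clustering out, not that the plan denies it.

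A reader might infer that the standard errors are certainly too small, or that the full cluster-trial design effect applies. The documents support neither. Use is a patient-level exposure, so inflation needs positive clustering of both use and outcome, and neither ICC is given. The full effect (SE ratio 1.48 by site, 2.04 by organization, at outcome ICC 0.10) would need use to be constant within clusters.

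A reader might also infer very strong clustering of use because organizations were randomized. The plan's own effect size does not carry that far. An arm difference of 0.352 SD adds between-cluster variance of (0.352/2)² = 0.031, an ICC contribution of about 0.03. Other differences between sites could add to it, but an exposure ICC of 0.30 has no source in the documents and serves only as an upper scenario. The 0.10 is likewise borrowed from the main trial's power calculation, where it is described as an ICC among sites. It is not an ICC for anxiety or loneliness.

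The survey is supplemental, observational and conducted once, and it aims to quantify an association. Zip code is collected in part to understand community spread, so some local information will be available. These facts lower the priority. They do not explain why the section's own handling of nesting stops short of these models.

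**Conclusion.** The point holds in conditional form. The survey models name no site, organization or arm term and no cluster-robust variance, although the respondents are nested and the same section handles nesting for Reach and retention. If use and outcome both cluster positively, intervals are likely too narrow. Modest inflation is the likelier case: type I error of about 0.06 to 0.09 with both ICCs between 0.05 and 0.10 by organization. It reaches 0.16 only under an unsourced exposure ICC of 0.30 combined with an outcome ICC of 0.10, and it stays at 0.05 if use does not cluster. Confounding by arm or organization is possible and is not quantified here.

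These figures rest on assumed ICCs, all 520 responding, equal clusters, exchangeable correlation and no covariates. This is a cheap improvement to a supplemental analysis. It does not bear on the primary comparison.

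**What to change.** Keep the same linear, logistic and log-binomial models and state three additions:

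1. Include arm as a covariate.
2. Account for clustering either with random intercepts for site within organization, or with organization-level cluster-robust standard errors and a small-sample correction, since there are only 16 clusters. For the logistic and log-binomial models the robust-variance route keeps the marginal estimand. Random intercepts would make it conditional on the cluster.
3. Fit organization fixed effects as a sensitivity analysis only. They remove all between-organization confounding, including arm, but discard between-organization variation in use, and a log-binomial model with 15 indicators may not converge.

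Report the estimated ICCs of use and of each outcome, so that the size of the correction is visible.

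The cost is somewhat wider intervals and a little more analysis work. No new data are needed: section 5 already collects downloads by site, and section 9 matches survey responses to app use.
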